APPENDIX 7: CYTOKINE RELEASE SYNDROME MANAGEMENT ALGORITHM

The following treatment management guidelines are provided for general guidance. These guidelines should not substitute for a more individualized, tailored approach to managing a patient experiencing cytokine release syndrome (CRS).

Cytokine Release Syndrome Management Measures/Algorithm

As a general principle, differential diagnoses should be diligently evaluated according to standard medical practice. Non-inflammatory etiologies should be considered and appropriately treated.

For patients with suspected CRS:

- For Grade 1 or Grade 2 events, implement supportive care, including management of isolated symptoms based on institutional practices.
- Consider admitting the patient for monitoring and providing supportive care, including management of isolated symptoms based on institutional practices and protocol management guidelines (e.g., hydration management guidelines, Section 5.4.2.2).
- For patients with a persistent or worsening clinical condition after initial treatment of CRS, reevaluate for other contributing conditions. It is particularly important to reassess the patient for coexisting infections and cardiac, pulmonary, thromboembolic, and other complications.

Grading Assessment per CTCAE v.5.0		Treatment Measures Recommended
Grade 3 CRS	
 • Hypotension managed with one pressor • Hypoxia requiring > 40% O₂ 	
 • Vasopressin administration should be considered if the hypotensive event is refractory to > 3L of fluid resuscitation • Oxygen therapy (nasal canula, non-invasive positive pressure ventilation, etc.) for respiratory symptoms with consideration of intubation for a patient with severe respiratory manifestations
Grade 4 CRS	
 • Life-threatening consequences • Pressor or ventilatory support indicated 	
 • Supportive care for renal, hepatic, and other organ function deteriorations • Steroid therapy should be considered (e.g., hydrocortisone 100 mg every 8 hours, dexamethasone 10 mg up to 4 times daily, methylprednisone 1-2 mg/kg/day IV or PO equivalent) • High-dose steroid (e.g., methylprednisolone 2 mg/kg up to 1 gram daily for 3 days) may be considered for severe CRS that failed to respond after repetitive steroid treatments • For severe CRS cases that require simultaneously aggressive management of hypotension, oxygenation, and cardiac telemetry, consult intensivist for ICU evaluation

Abbreviations: CRS = cytokine release syndrome; CTCAE = Common Terminology Criteria for Adverse Events; ICU = intensive care unit; IV = intravenous; O₂ = oxygen; po = orally

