- For future infusions, the following prophylactic premedications are recommended: diphenhydramine 50 mg (or equivalent) and/or acetaminophen/paracetamol 325 to 1000 mg administered at least 30 minutes before the infusion. If necessary, corticosteroids (up to 25 mg of methylprednisolone or equivalent) may be used (see [Appendix 5](#) for corticosteroid dose equivalents). Subsequent infusions may be administered at a reduced rate (e.g., 50% of the original infusion rate).

For **Grade 3 or Grade 4** symptoms (severe reaction, Grade 3: prolonged [i.e., not rapidly responsive to symptomatic medication and/or brief interruption of infusion]; recurrence of symptoms following initial improvement; hospitalization indicated for other clinical sequelae [e.g., renal impairment, pulmonary infiltrates]. Grade 4: life-threatening; pressor or ventilatory support indicated):

- Immediately discontinue infusion of NKTR-214 or nivolumab. Begin an IV infusion of normal saline and treat the patient as follows: recommend bronchodilators, epinephrine 0.2 to 1 mg of a 1:1000 solution for subcutaneous administration or 0.1 to 0.25 mg of a 1:10,000 solution injected slowly for IV administration, and/or diphenhydramine 50 mg IV with

methylprednisolone 100 mg IV (or equivalent), as needed. NKTR-214 or nivolumab will be permanently discontinued. The patient should be monitored until the Investigator is comfortable that the symptoms will not recur. Investigators should follow their institutional guidelines for the treatment of anaphylaxis. Remain at the bedside and monitor the patient until recovery of the symptoms.

In case of late-occurring hypersensitivity symptoms (e.g., appearance of a localized or generalized pruritus within 1 week after treatment), symptomatic treatment may be given (e.g., oral antihistamine or corticosteroids).

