5.14.1.1 NKTR-214 Combined with Nivolumab Discontinuation Criteria

Patients meeting any of the following criteria will be required to permanently discontinue all assigned study drug(s). However, per Investigator assessment, NKTR-214 or nivolumab may be

continued as a monotherapy if the toxicities listed below are considered related to only one of the study drugs, once the criteria to resume are met (Section 5.13.7). For CVA events and suspected TIA events, follow the criteria described below (additional details are provided in the CVA management algorithm in [Appendix 6](#)).

NKTR-214 combined with nivolumab treatment should be permanently discontinued for the following:

- Any \geq Grade 2 drug-related uveitis, eye pain or blurred vision that does not respond to topical therapy and does not improve to Grade 1 severity within the retreatment period OR requires systemic treatment
- Grade 3 or 4 infusion reaction of any duration that occurs during the:
 - NKTR-214 infusion or prior to the nivolumab infusion requires discontinuation of NKTR-214.
 - Nivolumab infusion or later requires discontinuation of both NKTR-214 and nivolumab.
- Any Grade 3 non-skin, drug-related AE lasting > 7 days or recurs, with the following exceptions for laboratory abnormalities, drug-related uveitis, pneumonitis, bronchospasm, neurologic toxicity, hypersensitivity reactions, and endocrinopathies
 - Grade 3 drug-related uveitis, pneumonitis, bronchospasm, neurologic toxicity, myocarditis, or hypersensitivity reaction of any duration requires discontinuation
 - Grade 3 drug-related endocrinopathies (excluding adrenal insufficiency) adequately controlled with only physiologic hormone replacement do not require discontinuation.
 - Note: For adrenal insufficiency of Grade ≥ 3 , treatment needs to be discontinued regardless of control with hormone replacement (hospitalization for diagnostic workup of adrenal insufficiency without severe symptoms should not require discontinuation).
 - Grade 3 drug-related laboratory abnormalities do not require treatment discontinuation except:
 - Grade 3 drug-related thrombocytopenia > 7 days or associated with bleeding requires discontinuation
 - Any drug-related LFT abnormality that meets the following criteria require discontinuation (also see Hepatic Adverse Event Management Algorithm, in nivolumab Investigator's Brochure):

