 - ◆ Treatment-emergent ALT or AST > 3 times ULN ($> 2 \times$ baseline AND $> 3 \times$ ULN for patients with baseline elevation) AND
 - ◆ Total bilirubin > 2 times ULN ($> 2 \times$ baseline AND $> 2 \times$ ULN for patients with baseline elevation) or clinical jaundice, without initial findings of cholestasis (e.g., elevated serum alkaline phosphatase) (see Section 8.10)

In most cases of Grade 3 AST or ALT elevation that do not improve with hepatic AE management, study treatment will be permanently discontinued (see Section 5.13 for more details). If the Investigator determines a possible favorable benefit/risk ratio that warrants continuation of study treatment, a discussion between the Investigator and the Medical Monitor must occur. For IL-2 mediated ALT/AST elevations $< 8.0 \times \text{ULN}$ in Cycle 1 only, study treatment does not need to be discontinued.

- Any Grade 4 drug-related adverse event or laboratory abnormality (including but not limited to creatinine, AST, ALT, or total bilirubin), except for the following events which do not require discontinuation:
 - Grade 4 neutropenia ≤ 7 days
 - Grade 4 lymphopenia or leukopenia or asymptomatic amylase or lipase
 - Isolated Grade 4 electrolyte imbalances/abnormalities that are not associated with clinical sequelae and are corrected with supplementation/appropriate management within 72 hours of their onset
 - Grade 4 drug-related endocrinopathy adverse events (except adrenal insufficiency or hypophysitis), such as, hyper- or hypothyroidism, or glucose intolerance, which resolve or are adequately controlled with physiologic hormone replacement (corticosteroids, thyroid hormones) or glucose-controlling agents, respectively, may not require discontinuation after discussion with and approval from the Medical Monitor.
 - Note: For Grade ≥ 3 adrenal insufficiency and/or Grade ≥ 4 hypophysitis, treatment needs to be discontinued regardless of control with hormone replacement (hospitalization for diagnostic workup of adrenal insufficiency without severe symptoms should not require discontinuation).
- Any event that leads to delay in dosing lasting > 8 weeks from the previous dose requires discontinuation, with the following exceptions:

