8.3 Grading of AEs

The severity of an event and the seriousness are not to be considered synonymous. The severity is grading the intensity of an event. The seriousness of event is based on the patient/event outcome or action criteria. All AEs will be assessed for severity using the National Cancer Institute (NCI) Common Terminology Criteria for Adverse Events (CTCAE) version 5.0 guidelines. If a particular AE is not listed in the NCI-CTCAE, the following criteria will be used:

- Grade 1 = Mild (event results in mild or transient discomfort, not requiring or needing only minimal intervention or treatment; does not limit or interfere with daily activities [e.g., insomnia, mild headache]).
- Grade 2 = Moderate (event is sufficiently discomforting so as to limit or interfere with daily activities; may require interventional treatment [e.g., fever requiring antipyretic medication]).
- Grade 3 = Severe (event results in significant symptoms that prevent normal daily activities; may require hospitalization or invasive intervention).
- Grade 4 = Life threatening or disabling.
- Grade 5 = Death.

AEs will be reported with an individual start and stop date for each level of severity.

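### Appendix 7 can be read to place one-pressor cytokine release syndrome in both Grade 3 and Grade 4, and for a short, non-recurrent drug-related event the two grades lead to opposite discontinuation outcomes

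*Protocol*

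**What the plan says.** The table in Protocol Appendix 7 is headed "Grading Assessment per CTCAE v.5.0". Its Grade 3 row has two bullets: "Hypotension managed with one pressor", and a hypoxia criterion. Its Grade 4 row also has two: "Life-threatening consequences" and "Pressor or ventilatory support indicated". Neither row says whether its bullets are alternatives or must all be met, and there is no rule for a patient who fits both rows. Section 5.13.8.2 directs investigators to this appendix for managing CRS.

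Section 8.3 sets the general grading rule: "All AEs will be assessed for severity using the National Cancer Institute (NCI) Common Terminology Criteria for Adverse Events (CTCAE) version 5.0 guidelines".

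Section 5.14.1.1 ties permanent discontinuation in Arm A to the grade. One trigger is "Any Grade 4 drug-related adverse event or laboratory abnormality", and CRS is not among its listed exceptions. Another is "Any Grade 3 non-skin, drug-related AE lasting > 7 days or recurs"; CRS is not among the Grade 3 events that stop treatment whatever their duration. The section opens by allowing one drug to continue alone if the toxicity is attributed only to the other.

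Sections 5.13.1 and 5.13.7 allow dosing to resume once the event has resolved to Grade 1 or baseline. Section 5.13.7 bars further study therapy for a patient who meets a permanent discontinuation criterion.

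**The concern.** Hypotension is an identified risk of NKTR-214 (Section 2.3.5) and a listed feature of CRS (Section 5.13.8.2), so a patient with CRS who needs one pressor is a foreseeable case. If that patient can be assigned either grade from the same table, two sites with the same clinical facts can reach opposite conclusions about whether the attributed drug may ever be given again. The discontinuation rule is mandatory and turns on the grade, so the ambiguity reaches a treatment decision.

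**Working it through.** No arithmetic applies. The check compares the two rows and then follows one case through the rules that use the grade.

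**Step 1. Do the rows overlap?** Take a patient with CRS whose hypotension is managed with one pressor and who does not meet the hypoxia criterion.

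- If bullets are alternatives in both rows, the patient meets Grade 3 (one pressor) and Grade 4 (a pressor is indicated). The rows overlap.
- If both Grade 4 bullets are required, a one-pressor patient whose condition is not life-threatening is Grade 3 only. The table does not state this. If the same convention applied to the Grade 3 row, that row would need a pressor and hypoxia together, and this patient would fit neither row.
- If the higher grade always applied under the alternatives reading, the one-pressor line under Grade 3 would never be used.

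**Step 2. Does the grade change the outcome?** Suppose the event is drug-related, resolves within 7 days and does not recur.

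| Rule | Read as Grade 3 | Read as Grade 4 |
|---|---|---|
| 5.14.1.1 | Discontinuation not required: not over 7 days, no recurrence, CRS not on the any-duration list | Permanent discontinuation required; CRS not an exception |
| 5.13.1 | NKTR-214 is delayed until Grade 1 or baseline, then may resume | The delay rule gives way to 5.14.1.1 |
| 5.13.7 | Resumption permitted after resolution | No further study therapy |

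The same facts give opposite results for the attributed drug. The Grade 3 path permits resumption but does not compel it: the investigator may still judge the risk too high.

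**Step 3. Where does the conflict stop?**

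- If the event lasts more than 7 days or recurs, both grades lead to discontinuation.
- If the event is not drug-related, neither of these two triggers applies.
- If the event is attributed to one drug only, 5.14.1.1 lets the other continue as monotherapy under either reading, and the conflict concerns the attributed drug alone.

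**Step 4. Does it reach the planned analyses?** SAP Section 8.1 presents adverse event summaries by worst grade with Grades 3 and 4 pooled, or as Grade 3 and above. SAP Table 6 plans only the time-to-onset summary for CRS, by any grade and Grade 3-5. None of these changes when an event moves between Grade 3 and Grade 4; only by-patient listings could show it. A different stopping decision would enter the discontinuation and exposure summaries as that decision.

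**Step 5. How many events?** Section 5.13.8.2 reports 5 patients with CRS after NKTR-214 exposure. Most events were Grade 1 or 2, and two were Grade 3 and resolved. It mentions no Grade 4 event, does not say whether a pressor was used, and gives no denominator. The expected number of one-pressor events in this trial cannot be derived from it.

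**The case against.** The strongest reply is that Appendix 7 describes itself as general guidance, that Section 8.3 makes CTCAE v5.0 the grading standard, and that 5.14.1.1 does not cite Appendix 7. An investigator would then grade from CTCAE and the appendix would not matter. This stands in part: the appendix is not the formal source of the grade. But its table presents its rows as that same grading, it is the only CRS grading text in the documents, and 5.13.8.2 sends investigators to it.

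Second, for suspected CRS of Grade 3 or higher, 5.13.8.2 encourages contact with the Medical Monitor. Both readings prompt that contact, which reduces divergence between sites. It is not a requirement and does not supply the missing rule.

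A reader might infer several stronger things that the documents do not support:

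- That every one-pressor event fits both grades. This holds only if the Grade 4 bullets are alternatives, which the table leaves open.
- That the grade decides all remaining Arm A treatment. The monotherapy provision in 5.14.1.1 rules this out when one drug alone is blamed, and Section 8.10 names CRS among events primarily related to NKTR-214.
- That 5.14.1.1 contradicts itself by allowing re-treatment. It only refrains from requiring discontinuation; permission to resume is in 5.13.1 and 5.13.7.
- That reported Grade 3 and Grade 4 CRS rates would be distorted. No planned summary table separates them.
- That one row departs from CTCAE v5.0. That source is not in the documents, so this cannot be checked.
- That Section 5.13.9 settles the matter because it defines a Grade 4 infusion reaction as "life-threatening; pressor or ventilatory support indicated". The wording is similar and may steer a reader toward Grade 4, but it concerns a different event, and there Grades 3 and 4 share one instruction.

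**Conclusion.** The two Appendix 7 rows are not mutually exclusive as written, and the overlap matters for one defined case: drug-related CRS with hypotension managed by one pressor, lasting 7 days or less, without recurrence. For that case the Grade 3 reading leaves the attributed drug open to resumption and the Grade 4 reading ends it permanently. The conclusion assumes that the Grade 4 bullets are alternatives, or at least that a site could reasonably read them so. The number of affected patients is unknown, probably small and possibly zero. The effect falls on individual treatment decisions, and the primary analyses do not depend on the grade. It is still worth correcting, because the rule it feeds is mandatory and the consequence for the individual patient is large.

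**What to change.** The sponsor's medical team should reconcile the Grade 3 and Grade 4 CRS rows in Appendix 7 with each other, and with the CTCAE v5.0 grading named in the table heading and Section 8.3. The rows should be mutually exclusive, state how the bullets within each combine, and lead to one outcome under 5.14.1.1, 5.13.1 and 5.13.7. Which grade a one-pressor event should carry, and what should follow from it, is for that team to decide. The cost is one table edit in the next amendment or a memo to sites; it needs no new data and no change to the design or the SAP.

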APPENDIX 8: INDUCERS AND STRONG INHIBITORS OF CYP3A4

Inducers and Strong Inhibitors of CYP3A4^a	
CYP3A4 Inducers	Phenytoin Carbamazepine Rifampin Rifabutin Rifapentine Phenobarbital Dexamethasone St. John's Wort
Strong CYP3A4 Inhibitors	Ketoconazole Itraconazole Posaconazole Voriconazole Clarithromycin Erythromycin Telithromycin Nefazodone Saquinavir Lopinavir/ritonavir Ritonavir Atazanavir Indinavir Nelfinavir Boceprevir Conivaptan

[Cabometyx, 2021](#); [Sutent, 2019](#)

- a. Notes: Lists may not be exhaustive. Grapefruit, grapefruit juice and other foods that are known to inhibit CYP3A4 activity should be avoided during treatment. St. John's Wort (*Hypericum perforatum*) is known to be an inducer of CYP3A4 and should be avoided during treatment.

APPENDIX 9: RESPONSE EVALUATION CRITERIA IN SOLID TUMORS GUIDELINES (VERSION 1.1) WITH BRISTOL-MEYERS SQUIBB MODIFICATIONS

1. EVALUATION OF LESIONS

Solid tumors will be evaluated using Response Evaluation Criteria In Solid Tumors version 1.1 (RECIST 1.1) guideline with Bristol-Meyers Squibb modifications ([Eisenhauer, 2009](#)).

At baseline, tumor lesions/lymph nodes will be categorized as measurable or non-measurable as follows:

1.1 Measurable

Tumor lesions: Must be accurately measured in at least one dimension (longest diameter in the plane of measurement is to be recorded) with a minimum size of:

10 mm by CT/MRI scan (scan slice thickness no greater than 5 mm), or $\geq 2x$ slice thickness if greater than 5mm.

Malignant lymph nodes: To be considered pathologically enlarged and measurable, a lymph node must be ≥ 15 mm in short axis when assessed by CT/MRI scan (scan slice thickness recommended to be no greater than 5 mm).

Lymph nodes merit special mention since they are normal anatomical structures which may be visible by imaging even if not involved by tumor. Pathological nodes which are defined as measurable and may be identified as target lesions must meet the criterion of a short axis of ≥ 15 mm by CT/MRI scan. Only the short axis of these nodes will contribute to the baseline sum. The short axis of the node is the diameter normally used by radiologists to judge if a node is involved by solid tumor. Nodal size is normally reported as two dimensions in the plane in which the image is obtained (for CT scan this is almost always the axial plane; for MRI the plane of acquisition may be axial, sagittal or coronal). The smaller of these measures is the short axis. For example, an abdominal node which is reported as being 20 mm x 30 mm has a short axis of 20 mm and qualifies as a malignant, measurable node. In this example, 20 mm should be recorded as the node measurement. All other pathological nodes (those with short axis ≥ 10 mm but < 15 mm) should be considered non-target lesions. Nodes that have a short axis < 10 mm are considered non-pathological and should not be recorded or followed.

Note: Lesions on X-Ray are not to be selected as Target or Non-Target Lesions.

1.2 Non-Measurable

All other lesions are considered non-measurable, including small lesions (longest diameter < 10 mm or pathological lymph nodes with ≥ 10 to < 15 mm short axis) as well as truly non-measurable lesions. Lesions considered truly non-measurable include: leptomenigeal

disease, inflammatory breast disease, lymphangitic involvement of skin or lung, abdominal masses/abdominal organomegaly identified by physical exam that is not measurable by reproducible imaging techniques.

Note: Lesions on X-Ray are not to be selected as Target or Non-Target Lesions.

1.3 Special Considerations Regarding Lesion Measurability

1.3.1 Bone lesions

- Bone scan, positron emission tomography (PET) scan and plain films are not considered adequate imaging techniques to measure bone lesions. However, these techniques can be used to confirm the presence or disappearance of bone lesions.
- Lytic bone lesions or mixed lytic-blastic lesions, with identifiable soft tissue components, that can be evaluated by cross sectional imaging techniques such as CT or MRI can be considered as measurable lesions if the soft tissue component meets the definition of measurability described above.
- Blastic bone lesions are non-measurable.

1.4 Baseline Documentation of ‘Target’ and ‘Non-Target’ Lesions

When more than one measurable lesion is present at baseline all lesions up to a maximum of 5 lesions total (and a maximum of two lesions per organ) representative of all involved organs should be identified as target lesions and will be recorded and measured at baseline (this means in instances where patients have only one or two organ sites involved a maximum of two and four lesions respectively will be recorded).

Note: A maximum of two lesions can be selected per organ system. For example, a maximum of two lung lesions can be selected (selected from one lung or one lesion from each). A maximum of two lymph nodes can be selected at baseline, as the lymphatic system is considered one organ.

Target lesions should be selected on the basis of their size (lesions with the longest diameter), be representative of all involved organs, but in addition should be those that lend themselves to reproducible repeated measurements. It may be the case that, on occasion, the largest lesion does not lend itself to reproducible measurement in which circumstance the next largest lesion which can be measured reproducibly should be selected.

A sum of the diameters (longest for non-nodal lesions, short axis for nodal lesions) for all target lesions will be calculated and reported as the baseline sum diameters. If lymph nodes are to be included in the sum, then as noted above, only the short axis is added into the sum. The baseline sum diameters will be used as reference to further characterize any objective tumor regression in the measurable dimension of the disease.

All other lesions (or sites of disease) including pathological lymph nodes should be identified as non-target lesions and should also be recorded at baseline. Measurements are not required and these lesions should be followed as ‘present’, ‘absent’, or in rare cases ‘unequivocal progression’ (more details to follow). In addition, it is possible to record multiple non-target lesions involving the same organ as a single item on the case record form (e.g., ‘multiple enlarged pelvic lymph nodes’ or ‘multiple liver metastases’).

